Accuracy and Precision Test of TempTraq® compared to Pulmonary Artery Catheter for Monitoring Temperature in Adults in Intensive Care Unit

7/7/2020

Principal Investigator:

- [name] Ph.D RN CNS, Senior Nurse Scientist, Office of Research & Innovation, Cleveland Clinic, [contact]

Co-Investigators:

- [name] DNP RN, Nurse Scientist, Office of Research & Innovation, Cleveland Clinic
- [name] MS, Biostatistician Quantitative Health Sciences, Lerner Institute, Cleveland Clinic

Introduction

Temperature monitoring is an important assessment tool for healthcare providers. Over the years a number of changes have been made to improve our ability to accurately and precisely measure and monitor a patient's temperature (Sund-Levander, & Grodzinsky, 2013). However, most of these new technologies have limitations and many provide readings that are too variable under different conditions and thus cannot be relied upon to provide a true measure of a patient's temperature. Inaccurate temperature monitoring can result in delayed treatment or administration of treatment not actually needed. To be useful a thermometer must demonstrate precision and accuracy.

Background

The gold standard against which all thermometer devices are compared is the core temperature as measured by the pulmonary artery (PA) catheter (Farnell et al. 2005). Although body temperature measured using a PA catheter is the most accurate measure to date, it is an invasive procedure and the risks of inserting and maintaining a PA catheter may not be justified (Pinsky, & Vincent, 2005). Chemical thermometers are a non-invasive method for obtaining a temperature orally, rectally, inguinal, or axillary. Chemical thermometers are affected by many variables and each route has different limitations. Previous studies identify accuracy and precision issues with chemical thermometers. Electronic thermometers (if calibrated often) are a bit more accurate; but they also have limitations. Some electronic thermometers are non-invasive (, oral, tympanic & temporal), but others require invasive methods to insert the thermistor (esophageal, rectal, or urinary bladder). None of these methods have been found to be as accurate or reliable for patients as the PA catheter temperature measurement (Farnell et al. 2005; Lawson, et al. 2007).

One alternative to the use of invasive temperature monitoring that may be more accurate and reliable than either chemical or electronic thermometers is the TempTraq® thermometer. This thermometer developed by Blue Spark Technologies (Westlake, Ohio) is applied to the skin as a patch. The TempTraq® thermometer is a thin, single-use, battery-powered skin patch that monitors and records skin temperature. Previous studies have demonstrated that it is reliable and accurate for monitoring temperature in children and in healthy adults. However, it has not been tested in ill adult patients.

Methods

Purpose

The purpose of this feasibility study is to assess the accuracy and precision of the Temp-Traq thermometer for monitoring body temperature in adult patients under three conditions (hypothermia, normothermia, and hyperthermia).

Specific Aims

1. To assess the accuracy of the Temp-Traq thermometer as compared to a gold standard (Core temp measured by Pulmonary Artery Catheter)
2. To assess the precision of the Temp-Traq thermometer over repeated measures
3. To determine if accuracy &/or precision is consistent in three conditions (hypothermia, normothermia, or hyperthermia)

Design

A repeated measures within-group comparative design will be used for this study.

Sample/Setting

To address the specific aims of this study we will identify patients (N = 40) who have a pulmonary artery (PA) catheter in place (patients in intensive care units). Letters of support are attached from the unit managers where the study will take place (see attached).

Inclusion Criteria

Adult patient (male or female) in intensive care unit who will have a PA catheter in place for at least the next 8 hours; and who have no visible skin condition to the axillary region upon inspection by the research nurse are eligible for this study

Exclusion Criteria

1. Patients younger than 21
2. Patients who will not have a PA catheter in place for the next 8 hours
3. Patients who have a visible skin condition to the axillary region upon inspection by

the research nurse

4. Patients who will be going for procedures or for some reason will not be available for the 6 hours of the study

Procedure

Once a patient is identified, the researcher will record basic demographic data (see data collection form attached) and the axillary area will be assessed for visible signs of any skin conditions. If there are no visible signs of a skin condition the researcher will apply the Temp-Traq thermometer to the right or left axilla of the subject and record the location of the placement. The researcher will record both the PA and Temp-Traq recordings of subject's temperature (taken at the same time) on the data collection form (see attachment) at four data points; baseline (5 minutes post application of Temp-Traq) and every two hours (+/- 15 minutes) after baseline X 3 (See Protocol attachment).

Previous testing of the TempTraq® on children and healthy adults has not resulted in any adverse skin reactions. However, as this is a new thermometer format and there is not a significant body of literature on potential skin reactions, we will assess skin before and after application. Thus, at the end of the last reading the Temp-Traq thermometer will be removed and the skin will be assessed for erythema. If erythema is present the patient's nurse and physician will be notified by the researcher.

Protection of Human Subjects

Since non-invasive temperature monitoring poses no risk to patients and is part of usual care and since we will not collect or record any protected health information (PHI), written informed consent will not be sought. Patients will be identified by their study ID number only. The data will be collected by a registered nurse data collector familiar with the intensive care setting and data will be stored in a locked file cabinet in the researchers locked office. Temperature data for the Temp-Traq is collected through the Temp-Traq Application (AP) which will be placed on a Cleveland Clinic Approved and encrypted i-pad. Once the study is completed and all data has been transferred to the study database, the Temp-Traq application and all of its data will be deleted from the i-pad.

Analysis

We will use the TOST (Two One Sided t-tests) method for equivalence testing. This method requires a defined range of mean differences between two test methods, an estimate of the precision of the measurement of the two systems, and an estimate of the size of the possible difference in the means of the two methods under consideration. The TOST null hypothesis is a joint null hypothesis that the mean measurement differences between the two methods is greater than a critical lower bound and less than a critical upper bound. If the null is rejected then we can conclude that the absolute difference of the means for the two groups falls within the specified range. It was determined that to be considered equivalent with respect to accuracy the mean

measurements of the two methods should be within ± 0.2 degrees of each other. Precision tests for Temp-Traq thermometer using accepted ASTM test methods for various combinations of temperature and humidity provided a range of measurement variation between .0000435 and .019928 with a mean of 0.000254500. If we assume both test methods exhibit the same levels of precision then the variance of the differences between their two means will reduce to two times the values listed previously. This will result in estimates of the standard deviations of the mean differences of .0093, .032, and .063 respectively.

The two methods for body temperature that will be examined are core temperature measurements with a PA catheter and temperature measurements using the Temp-Traq. Paired temperature measurements for both methods will be taken simultaneously every 2 hours for a 6 hour period. This will provide 4 repeated temperature measures per patient. The simultaneous measurements within a given patient should exhibit a high degree of correlation. If .7 is chosen as the lower bound for the correlation between the paired readings (higher correlations would result in an estimate of fewer patient samples thus the choice of .7 is conservative) and if the average standard deviation of the mean of the differences is used as an estimate of the expected variability, then it would be possible to declare measurement equivalence for a difference of $\pm .19$ with a sample size of 40 patients. This assumes the ASTM measurements of instrument variation are representative of the within patient variance. Given the vagaries of patient-to-patient this may be too optimistic an estimate. Table 1 (attached) is a summary of patient sample sizes for standard deviations equal to the average standard deviation and for 5 and 10 fold increases in this value.

A sample size of 40 patients will provide 80% or greater power for testing for equivalence between methods where the mean difference is .1 or less for up to a ten-fold increase in the estimates of the variability of the differences based on the ASTM precision measures and for a mean difference of .15 for up to a five-fold increase in these same measures. If the sample size is 40 then the power for the test of equivalence, where the difference is .15 and the standard deviation is a ten-fold increase, is 35%. Agreement testing: The Bland-Altman test will be used to test the agreement of the two methods. This test will permit a check for significance of bias between the two measures (the average difference between the two measures) as well as a check for significant trending over the range of the measurements. If the bias is significant then the results of the two differ by an overall offset in their measurements. If the trending (slope of the regression line) is significant then the difference between the two measurements changes as their magnitude changes which means the two methods are not in agreement.

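### Aim 3 concerns consistency across hypothermia, normothermia and hyperthermia, but the Analysis plans only pooled tests: a slope partly covers accuracy, and nothing compares precision by condition

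*Combined protocol and SAP*

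**What the plan says.** The Purpose section states "The purpose of this feasibility study is to assess the accuracy and precision of the Temp-Traq thermometer" and names three conditions: hypothermia, normothermia and hyperthermia. Specific Aim 3 is "To determine if accuracy &/or precision is consistent in three conditions (hypothermia, normothermia, or hyperthermia". The Introduction gives the motive. Of newer thermometers it says that "many provide readings that are too variable under different conditions and thus cannot be relied upon", and it warns that "Inaccurate temperature monitoring can result in delayed treatment or administration of treatment not actually needed".

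Under Procedure, "The researcher will record both the PA and Temp-Traq recordings" at four time points, so every Temp-Traq reading has a simultaneous PA reading.

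The Analysis section plans three things:
- a TOST, under which the mean "measurements of the two methods should be within ± 0.2 degrees of each other";
- a Bland-Altman check of the overall bias, with a significant result interpreted as a constant offset between the methods;
- a Bland-Altman check for a linear trend of the difference over the measured range.

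Power is stated for all 40 patients together: "80% or greater power for testing for equivalence between methods where the mean difference is .1 or less" for up to a ten-fold increase in variability, and also for a difference of .15 at five-fold. The text gives no temperature bands, no target number per condition, no estimate by condition and no comparison of spread. It cites a data collection form, a protocol attachment and Table 1, none of which was available to me.

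**The concern.** The three conditions define the study's purpose, yet the analysis as written would produce one pooled verdict. Eligibility has no temperature criterion, so most readings may be normothermic. A pooled finding of equivalence within 0.2 could then be read as covering hypothermia and hyperthermia, where an error is most likely to mislead care.

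The slope check is a real but partial safeguard. It looks for one shape of inconsistency, a straight-line change in the mean difference. Errors in the same direction at both extremes largely cancel out of it, and an error at one extreme only may be missed. The overall bias check does not fill the gap, because the plan interprets a significant bias as applying everywhere. None of the three checks is designed to compare spread between conditions.

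**Working it through.** **1. The plan's own power figures.** Inputs from Analysis: average SD .032, paired correlation .7, margin ±0.2, n = 40. Alpha is not stated; I assume .05 for each one-sided test. The SD of the differences that reproduces the plan is

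fold × .032 × √(2(1 − .7)) = fold × .032 × .7746.

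| Fold | SD | True difference | Plan's power | Reproduced |
|---|---|---|---|---|
| 5 | .124 | .15 | 80% or more | 81% |
| 10 | .248 | .10 | 80% or more | 81% |
| 10 | .248 | .15 | 35% | 35% |

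All the figures match one test of 40 patients. With about 13 patients in a condition (an assumed even split), the powers in these three rows would be 39%, 39% and 17%.

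**2. What a linear slope can see.** The fitted slope is Σ(x − x̄)d / Σ(x − x̄)². Suppose equal numbers m lie a distance δ below and above the centre, each with error e. The numerator is then −mδe + mδe = 0. Example: 4 readings at 34.5, 32 at 37 and 4 at 39.5, with error −.4 at both extremes and 0 between. The slope is 0 and the pooled mean is 8 × (−.4)/40 = −.08, well inside ±0.2.

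**3. Pooled mean for a .4 error at both extremes.**
- 6/28/6 patients: 12 × .4/40 = .12
- 3/34/3: 6 × .4/40 = .06
- 10/20/10: 20 × .4/40 = .20, which is on the margin, so TOST nearly always fails

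**4. Simulation of the planned tests.** There were 20,000 trials per case, with 40 patients analysed on patient means (the plan does not say patient means or pairs). The following are assumptions:
- error patterns and patient mixes;
- condition centres 35.5/37.0/38.5;
- between-patient temperature SD .3 and within-patient SD .2;
- a patient's four differences perfectly correlated.

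Ranges cover two further choices. Either the PA reading is error-free or it shares the error equally ("If we assume both test methods exhibit the same levels of precision"). The slope is fitted either on the average of the two methods or on PA. For a same-direction error of .4:

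| Mix | Outcome | Ten-fold SD | Five-fold SD |
|---|---|---|---|
| 6/28/6 | (a) nothing flags it | 24–28% | under 1% |
| 6/28/6 | (b) TOST passes, slope not significant | 41–47% | 82–85% |
| 3/34/3 | (a) | 60–76% | 47–51% |
| 3/34/3 | (b) | 73–92% | 93–99% |
| 10/20/10 | (b) | under 2% | under 2% |

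Outcome (a) means that TOST passes and neither bias nor slope is significant. Outcome (b) also includes trials with a significant bias, which the plan would read as a general offset.

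Other patterns with 6/28/6, for outcome (a):
- opposite-direction error: under 5% at ten-fold, 0% at five-fold;
- error in hypothermia only: 5–59% at ten-fold, 0–3% at five-fold, depending on sign, axis and error share.

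If the correlation of a patient's differences is .5 instead of 1, same-direction (a) with 6/28/6 at ten-fold falls to 13–14%, while (b) rises to 55–60%.

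**5. Comparison with no error.** With 6/28/6 and zero error everywhere, (b) is 86–95% across the two SDs. At five-fold SD, the combination of a passed TOST and no slope is therefore almost as common with a .4 error at the extremes (82–85%) as without one.

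**6. Precision.** With the SD doubled at both extremes and no bias, TOST passes in 95–99% of trials (ten-fold) and 100% (five-fold). That is the correct answer about the mean. It confirms only that TOST is silent on spread. On the slope axis that otherwise gives 5%, significance rises to 16–21%, but the plan would read it as a changing difference, not as lost precision.

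**The case against.** Five points can be made for the plan.

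- *The wording of Aim 3 is loose.* Its and/or could be met by accuracy alone, and the slope is a planned test of whether error changes with temperature. This is fair for accuracy in part. But the Purpose names both properties, and only one shape of inconsistency in accuracy is tested.
- *The attachments may define bands.* This stands as a limit on what can be said. Even so, the Analysis text describes no comparison that would use them.
- *The main example is one that a straight line cannot see.* True, and its size and patient mix are assumed. Opposite errors with 6 patients at each extreme are caught, and so are same-direction errors with 10.
- *Outcome (b) counts trials in which the bias test fired.* Correct: with 6/28/6 at five-fold SD, bias is significant in 99% of trials. The fault there lies in interpretation, not detection. A high (b) alone also proves nothing, as step 5 shows; what matters is how little it changes when error is added.
- *Small groups give imprecise estimates, and this is a feasibility study.* Both stand. They argue for estimates instead of tests by condition, and for restraint in the claim. They do not argue for leaving a stated aim without an analysis.

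**Conclusion.** The concern holds. Followed exactly, the text available leaves consistency of precision unexamined and consistency of accuracy only partly examined. The precision gap follows from reading the plan and needs no simulation. The accuracy gap depends on how many patients fall at the extremes and on the shape of the error. For a .4 error in the same direction at both extremes, it is large with 3 patients at each and negligible with 10. With 6 at each, a pass with no slope occurs in 41–47% of trials at ten-fold SD and 82–85% at five-fold, although at five-fold the bias test nearly always fires and would be read as a general offset. The two SDs are the plan's own scenarios. The mixes, error sizes, temperature centres and correlation are assumptions. This should be changed, but it does not invalidate the pooled test.

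**What to change.** 1. Classify each pair by its recorded PA temperature into three bands, which the investigators fix before the data are seen.
2. For each band report the number of patients and pairs; the bias with a 90% CI set against ±0.2, using one mean per patient per band; and the SD and limits of agreement, combining between- and within-patient variance.
3. Compare bias across bands with a condition term in a model with a patient effect. Error in the PA reading can move pairs between bands and create false differences. In simulation with zero bias and shared error, the term was significant in .05–.08 of trials at five-fold SD, but in .09–.15 (6/28/6) and .10–.23 (3/34/3) at ten-fold. So repeat the comparison on patient means, with patients banded by mean PA temperature. That check gave .045–.075 under zero bias and detected the same-direction error in .969–1.000 (6/28/6) and .835–1.000 (3/34/3).
4. Present the SD by band as an estimate, not a test. With 6/28/6, the estimated hypothermic-to-normothermic SD ratio ran from .96 to 2.96 (5th–95th percentile) when truly doubled, and from .54 to 1.54 when equal.
5. Keep the slope check and state its x-axis.
6. State that the 80% power applies only to the pooled 40-patient test, and make no equivalence claim for a condition with few readings. With 3/34/3 and zero bias, at least one extreme was estimated beyond .2 in up to 22.9% of trials.

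The cost is one table, one model term and one check on data already being recorded, with no change to recruitment. The downsides are slightly more analysis, imprecise SDs where readings are sparse and a narrower claim there.

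### Skin eligibility rests only on what is visible, so a patient with a known adhesive or patch-material sensitivity and normal-looking axillae can receive the patch

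*Combined protocol and SAP*

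**What the plan says.** **Eligibility.** Under Inclusion Criteria, adults with a qualifying catheter "who have no visible skin condition to the axillary region upon inspection by the research nurse are eligible for this study". Exclusion item 3 is the mirror image and removes "Patients who have a visible skin condition to the axillary region upon inspection by" the research nurse. The other three exclusions concern age, how long the catheter will stay in, and availability for the study period.

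**Application.** The Procedure uses the same test: "If there are no visible signs of a skin condition the researcher will apply the Temp-Traq thermometer to the right or left axilla".

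**Device.** The Background says that the thermometer "is a thin, single-use, battery-powered skin patch that monitors and records skin temperature". It adds that the device has been studied in children and healthy adults, and not yet in adults who are ill.

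**Skin reactions.** The Procedure reports: "Previous testing of the TempTraq® on children and healthy adults has not resulted in any adverse skin reactions". It then gives its reason for looking at the skin before and after wear: "as this is a new thermometer format and there is not a significant body of literature on potential skin reactions". After the last reading the patch comes off and the skin is examined for erythema. If there is any, the patient's nurse and physician are told.

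**Consent.** Protection of Human Subjects explains why written consent is not sought: "Since non-invasive temperature monitoring poses no risk to patients and is part of usual care". It gives a further ground, that no protected health information is collected.

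**The concern.** The plan takes a precaution against skin reactions, and its eligibility rules look at the skin for the same evident purpose. Those rules see only the present state of the axilla. A contact sensitivity need leave no mark on skin that has not been exposed, so inspection misses the patients whose reaction is easiest to foresee. Their history may already be in the chart.

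What is at stake is an avoidable local reaction in a patient who could have been identified beforehand. There is also a question of consistency. One section treats monitoring as free of risk, while the section before it takes a precaution because the patch is new. An ethics committee reading both would not know which account of skin risk the investigators hold.

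**Working it through.** The plan gives no figure on this point, so there is none to reproduce. The check is mainly a comparison of the text.

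**Step 1. Follow a hypothetical patient through the rules.** Take an adult over 21 with a catheter in place for the next 8 hours, no procedures planned, a charted sensitivity to adhesive, and axillae that look normal.

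| Rule | Section | Result |
|---|---|---|
| No visible axillary skin condition | Inclusion Criteria | Met |
| Younger than 21 | Exclusion item 1 | Not excluded |
| Catheter not in place for the next 8 hours | Exclusion item 2 | Not excluded |
| Visible axillary skin condition | Exclusion item 3 | Not excluded |
| Unavailable during the study | Exclusion item 4 | Not excluded |
| Apply the patch if nothing is visible | Procedure | Patch applied |

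Allergy, adhesive sensitivity and tape sensitivity are not mentioned anywhere in the supplied text. Nor is a chart check for them.

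**Step 2. Length of exposure.** The baseline reading is 5 minutes after application. Three more follow at two-hour intervals, and the patch is removed after the last: 5 min + 3 × 2 h = 6 h 5 min, or about 6 hours, with a 15-minute window either way on the follow-up readings.

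**Step 3. Do the existing safeguards close the gap?**
- The check before application is the same visual inspection.
- The check at removal comes after the whole exposure. It can trigger notification of clinicians but cannot prevent a reaction.
- The earlier testing without reactions was in children and healthy adults, and the plan itself still added skin checks.

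**Step 4. How often might this arise?** The documents give no prevalence p of documented sensitivity, so the values below are assumptions. For 40 patients:
- chance that at least one has it = 1 − (1 − p)^40
- expected number removed by an exclusion, per 40 screened = 40 × p

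| Assumed p | At least one in 40 | Expected number per 40 screened |
|---|---|---|
| 0.5% | 1 − 0.995^40 = 18% | 0.2 |
| 1% | 1 − 0.99^40 = 33% | 0.4 |
| 2% | 1 − 0.98^40 = 55% | 0.8 |
| 5% | 1 − 0.95^40 = 87% | 2 |

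The middle column is the chance of enrolling someone with a recorded sensitivity. It is not the chance of a reaction to this patch. The last column is the more useful one, because it shows what an added exclusion would cost.

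**Step 5. Compare the two statements on risk.** Protection of Human Subjects speaks of non-invasive temperature monitoring in general and assigns it no risk. The Procedure speaks of this particular patch and takes a precaution because its skin effects are little documented. The general statement is then used to support not seeking written consent for a study of this patch. The two accounts are in tension and need one agreed wording.

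**The case against.** The strongest reply is that the exposure is slight: one single-use, non-invasive patch worn for about 6 hours, with no reactions in earlier testing, skin checked before and after, and clinicians told of any erythema. The data collector is a registered nurse who knows intensive care and might well act on a charted allergy without being told to. The data collection form and the Protocol attachment are cited but not supplied, and either could already contain an allergy item. All of this stands. It limits the size of the point, but the eligibility criteria and the application rule, followed as written, still admit the patient in Step 1.

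Several stronger readings are tempting, and the documents do not support them:

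- A reader might infer that many of these patients are sedated and cannot report an allergy. The plan does not mention sedation, and the point does not need it, because a chart check works either way.
- A reader might infer that erythema in a sensitive patient would distort a safety result. There is no skin-safety aim, endpoint or analysis. The aims are accuracy, precision and consistency across temperature conditions, and the analysis is TOST and Bland-Altman.
- A reader might take the 18% to 87% range as a measure of harm. It follows entirely from assumed prevalences and counts enrolment, not reactions.
- A reader might conclude that written consent is set aside only because the study is called risk-free. That is one of three stated grounds, with usual care and the absence of protected health information.
- A reader might call the two risk statements a flat contradiction. One is about monitoring in general and the other about this format, so tension is the fairer word.

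The word adhesive does not appear in the documents. That the patch sticks by adhesive is a reasonable inference from its being applied to the skin and worn for hours.

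**Conclusion.** The point holds as a cheap improvement to patient safety. In the supplied text, inspection is the only skin screen, and a patient with a known adhesive or patch-material sensitivity and normal-looking axillae passes it. The likely harm is minor and local, and its frequency cannot be estimated from the documents. Accuracy, precision, the equivalence test, the agreement analysis and the sample size of 40 are untouched.

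The conclusion rests on two assumptions: that the patch is held on by an adhesive or other material to which a patient can be sensitive, and that neither of the two unsupplied attachments already contains an allergy check. If one does, what remains is to carry that check into the eligibility criteria. The need to reconcile the two statements on risk depends on neither assumption.

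**What to change.** 1. Add a fifth exclusion: known or documented allergy or sensitivity to medical adhesive, tape or the materials of the patch. Check it before application in the chart's allergy entry, or by asking the patient or bedside nurse. If the data collection form or Protocol attachment already includes this, refer to it in Exclusion Criteria and in the Procedure's application step.
2. Reconcile the no-risk statement in Protection of Human Subjects with the Procedure's precaution, so that both sections and the eligibility criteria give the same account of skin risk from this patch.

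**Cost.** One line of text, one yes/no check when the researcher is already recording demographics and inspecting the axilla, and an edit to one sentence. A yes/no answer under the study ID need add no identifying data. The downside is a few more screen failures, about 0.2 to 2 per 40 screened at the assumed prevalences of 0.5% to 5%. Replacing them keeps the sample at 40, and the analysis does not change.

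### The skin check is broad before the patch goes on but names only erythema when it comes off, and the visible plan reports no skin result

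*Combined protocol and SAP*

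**What the plan says.** The relevant text is almost all in the Procedure section of the combined protocol and SAP.

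- **Reason for the check.** The protocol explains that "there is not a significant body of literature on potential skin reactions, we will assess skin before and after application".
- **Before application.** The Procedure says "the axillary area will be assessed for visible signs of any skin conditions". This is also an eligibility screen. The third exclusion criterion covers "Patients who have a visible skin condition to the axillary region upon inspection by" the research nurse.
- **Site.** The researcher is to "apply the Temp-Traq thermometer to the right or left axilla of the subject and record the location of the placement". No inspection of the other axilla is described.
- **After removal.** Once the final reading is done, "the Temp-Traq thermometer will be removed and the skin will be assessed for erythema". If erythema is found, the patient's nurse and physician are told. No other finding is named, and no later skin check is described.
- **Use of the result.** The three Specific Aims concern accuracy, precision and their consistency across three temperature conditions. The Analysis covers TOST, Bland-Altman and sample size. Neither mentions skin. The Procedure cites a data collection form and a protocol attachment that are not part of the text under review.

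**The concern.** A before-and-after comparison works when the same thing is looked for at both times. Here the second look is narrower than the first, and narrower than the reason given for having it, which is skin reactions in general. A visible change other than redness would have kept a patient out at baseline, yet the instructions at removal do not ask about it.

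This is the only safety assessment the documents describe, in a population in which the Background says the device is untested. A sign that is not looked for at removal cannot be recovered later, whereas an analysis can be rerun. If the result is also not summarised, the study will end with little it can say about skin tolerance in ill adults, although every patched patient is to be inspected.

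**Working it through.** The plan gives no figure for skin reactions, so there is none to reproduce. The check is a side-by-side reading, followed by what the planned sample could show.

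**1. The two inspections compared**

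| Feature | Before application | After removal |
|---|---|---|
| What is looked for | Any visible skin condition | Erythema |
| Where | Axilla | Skin after patch removal; other axilla not mentioned |
| Consequence of a finding | Exclusion | Nurse and physician notified |
| Place in Aims or Analysis | None (eligibility only) | None |

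The mismatch is in the first row. Non-erythematous changes fall within the first definition and outside the second.

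**2. Redness from other causes**

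Patients with a visible axillary condition are excluded, so redness already present is dealt with. The open question is new redness over the wear period, which is about 5 minutes + 3 × 2 hours, or roughly 6 hours. Looking only at the patched side does not help to separate a local reaction from generalised redness. Hyperthermia is one of the three conditions under study, so generalised redness is plausible.

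**3. What 40 patients could show**

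Input: n = 40 (Sample/Setting), assuming all 40 are patched and inspected at removal.

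The exact (Clopper-Pearson) two-sided 95% upper limit for 0 events is 1 − 0.025^(1/n):

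1 − 0.025^(1/40) = 1 − 0.9119 = 0.088, or 8.8%.

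Other possible results by the same method:

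| Patients with a new change | Exact 95% interval |
|---|---|
| 0/40 | 0% to 8.8% |
| 1/40 | 0.06% to 13.2% |
| 2/40 | 0.6% to 16.9% |
| 4/40 | 2.8% to 23.7% |

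**4. Illustration with assumed rates**

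The documents give no rate of non-erythematous change, so these values of r are assumptions. The expected number is 40r, and the chance that at least one occurs is 1 − (1 − r)^40.

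| Assumed r | Expected in 40 | Chance of at least one |
|---|---|---|
| 2% | 0.8 | 55% |
| 5% | 2 | 87% |
| 10% | 4 | 98.5% |

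These are chances that such a change *occurs*. They are not chances that it is missed, because a nurse may report it unprompted.

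**The case against.** The best defence is that skin is not a study aim. This is a feasibility study of accuracy and precision, and the inspection at removal is a bedside precaution. The first check is broad because it screens for eligibility; the second looks for the likeliest sign of a patch reaction. The protocol states a general commitment to assess skin before it names erythema, and the data collector is a registered nurse familiar with intensive care. Earlier testing in other populations is reported to have produced no adverse skin reactions.

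Much of this stands, and it rules out several stronger readings that a reader might infer:

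- *That a blister or skin tear would be scored as no finding and nobody told.* The documents show only that such changes are not prompted for and need not be recorded.
- *That redness in both axillae would be wrongly counted as a patch reaction.* The plan has no attribution rule and no count, so nothing is misattributed. The redness simply could not be told apart from a local reaction.
- *That the check is meant to support a statement of skin safety in ill adults.* No such statement is planned.
- *That no skin result will be collected.* The data collection form may contain a skin field.
- *That erythema leaves out most kinds of reaction.* The documents give no frequencies by type.

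The defence does not explain why a check added for skin reactions in general should narrow to one sign at the moment a reaction could be seen. A nurse's initiative is also no substitute for a recorded field completed the same way for every patient.

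**Conclusion.** The point holds in a limited form. The skin check at removal is narrower than both its own baseline and its stated purpose, and no skin result appears in the visible Aims or Analysis. The change is worth making because it costs little and the observation cannot be recovered afterwards. It is not a threat to the trial: sample size, power and the accuracy and precision conclusions do not depend on it.

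Its size cannot be put as a number of missed reactions, since every rate above is assumed. The firm figure is the 8.8% upper limit for 0/40, which rests on all 40 patients being patched and inspected; fewer would give a higher limit. The statement about missing results is confined to the text available, because the data form and protocol attachment could not be read.

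**What to change.** **Procedure.** Use one skin checklist before application and after removal. After removal, record any new visible change at the patch site relative to the pre-application record, with erythema as one listed item alongside others such as swelling, blister and skin tear. Complete it for every patched patient, including those with no finding. The same nurse can note the unpatched axilla at both times, to help separate generalised redness from a local reaction.

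**Analysis.** Add one descriptive line: the number and proportion of patched patients with a new patch-site change, with an exact 95% confidence interval.

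**For the sponsor to reconcile.** The notification sentence refers to erythema only, while the stated purpose is skin reactions generally. The two should be brought into line; which findings lead to notification is for the sponsor to decide.

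**Cost.** A slightly longer inspection and form, one line of analysis, and possibly a few more minor findings recorded. No extra patients or study time points are needed. The change should be in place before enrolment, or applied to the patients still to be enrolled.
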